11. STATISTICAL METHODS

Subjects enrolled in this study will be self-selected as they will be provided the option to participate in this study upon completion of treatment in a Phase 1b or Phase 2 study with JNJ-54861911.

Statistical analysis will be done by the sponsor or under the authority of the sponsor. A general description of the statistical methods to be used to analyze the efficacy and safety data is outlined below. Descriptive statistical analyses will be performed for all subjects receiving at least one dose of study drug in this study. Analyses may be performed separately for both DB and OL treatment phases. After all subjects have completed the DB treatment phase, a database lock for the DB treatment phase will take place upon which unblinded statistical analyses may be generated, and a study report for DB treatment phase may be prepared. Analyses may be performed separately for subgroups of subjects according to previous study participation as well as for the combined population of all subjects participating in this study, where appropriate. Summaries may also be presented by baseline CDR global score.

11.1. Subject Information

For all subjects who receive at least one dose of study drug descriptive statistics will be provided.

11.2. Sample Size Determination

The study is not powered according to statistical calculations. The number of subjects enrolled will depend on the number of subjects from other JNJ-54861911 studies who are willing to enroll in this extension study.

11.3. Pharmacokinetic Analyses and Pharmacokinetic/Pharmacodynamic Analysis

Population PK modeling of plasma and, if possible, CSF concentrations of JNJ-54861911 will be undertaken. In view of the sparse sampling foreseen for this study, data may be combined with a selection of Phase 1, Phase 1b, and Phase 2 data (e.g., from studies 54861911ALZ1001, 54861911ALZ1002, 54861911ALZ1005, and/or 54861911ALZ2002) in order to support a relevant structural model.

PopPK/PD analysis of biomarkers and/or cognitive markers may also be performed, and a suitable dose- and/or exposure-response model may be developed. If necessary or relevant for the analysis, Phase 1 and Phase 2 data may be integrated to inform the model structure or key parameter values.

A snapshot date for PK samples to be analyzed may be defined, if required, and documented in a data transfer plan (DTP) according to the applicable standard operating procedures and work instructions. Samples collected before this date will be analyzed for JNJ-54861911 and included in the population PK analysis. Samples collected after the snapshot date will be analyzed at a later date, and may be included in a population PK re-analysis when they become available after database lock.

Details of the analyses will be described in a PopPK/PD analysis plan and results will be provided in a separate report.

11.4. Pharmacodynamic Analyses

11.4.1. Biomarker Analyses

11.4.1.1. Fluid Biomarkers

Percent changes from baseline in CSF A β species (A β ₁₋₃₇, A β ₁₋₃₈, A β ₁₋₄₀, A β ₁₋₄₂) and sAPP total, as well as fragments (sAPP α , sAPP β) will be summarized at each scheduled time point using descriptive statistics and presented graphically by treatment period and treatment group.

Similar analyses will be performed for plasma A β ₁₋₄₀ and sAPP total, as well as fragments (sAPP α , sAPP β).

Exploratory analyses may be performed for CSF p-tau, t-tau and additional downstream biomarkers of neuroinflammation, neurodegeneration, and neuronal injury. Results of these analyses may be presented in a separate report.

11.4.1.2. Imaging Biomarkers

Changes from baseline in brain volumes and cortical thickness (regional and global) as measured by volumetric MRI will be summarized using descriptive statistics.

11.4.2. Cognition, Function and Clinical Status

Cognitive evaluations (RBANS, MMSE, and CVLT-II) and functional measures (Cognitive Function Index [CFI]) will be applied in this study at different time points as indicated in the Time and Events Schedule to explore the subject's cognitive performance/progression and function over time.

In addition during course of the study the subject's clinical status will be assessed regularly by means of the Clinical Dementia Rating Scale as indicated in the Time and Events Schedule.

Measurements will be summarized at each scheduled time point using descriptive statistics.

11.5. Safety Analyses

All subjects receiving at least one dose of study drug will be included in the safety analysis. Descriptive statistics will be computed.

Adverse Events

The verbatim terms used in the CRF by investigators to identify adverse events will be coded using the Medical Dictionary for Regulatory Activities (MedDRA). All reported adverse events with onset during the treatment phase (i.e., treatment-emergent adverse events, and adverse events that have worsened since baseline) will be included in the analysis. For each adverse event, the percentage of subjects who experience at least one occurrence of the given event will be summarized by treatment group. Adverse events will also be tabulated by severity and by relationship to study drug and will be presented by treatment group. Serious adverse events will be summarized separately.

Summaries will be provided for all subjects receiving at least one dose of study drug in this study, and will include adverse events from this study as well as any preceding studies (e.g., study JNJ-54861911ALZ1005, JNJ-54861911ALZ2002 or any future Phase 1b or Phase 2 JNJ-54861911 clinical studies) as applicable for subjects who previously participated in that study, where appropriate.

Summaries, listings, datasets, or subject narratives may be provided, as appropriate, for those subjects who die, who withdraw due to an adverse event, or who experience a severe or a serious adverse event. Subjects with AESIs may be counted or listed.

Clinical Laboratory Tests

Laboratory data will be summarized by type of laboratory test. Descriptive statistics will be calculated for each laboratory analyte at baseline and at each scheduled time point, and for changes from baseline.

The number and percentage of subjects experiencing a laboratory result below or above normal reference ranges will be provided for each laboratory analyte by treatment group.

A listing of subjects with any laboratory result outside the reference ranges will be provided.

Electrocardiogram (ECG)

Heart rate and ECG intervals (RR, PR, QRS, and QT) as well as corrected QT intervals according to Bazett's formula (QTcB) and Fridericia's formula (QTcF) from the 12-lead ECG will be summarized at baseline and at each scheduled time point and for changes from baseline using descriptive statistics.

The number and percentage of subjects with at least 1 occurrence of a treatment-emergent potentially clinically important QTc measurement (QTc value >450, >480, or >500 ms) or with a change from baseline in QTc >30 ms will be summarized by treatment group.

Data listings of subjects with any potentially clinically important values (QTc value >450, >480, or >500 ms) or with a change from baseline in QTc >30 ms will be provided.

Vital Signs

Descriptive statistics of pulse, blood pressure (systolic and diastolic) (supine and standing), temperature and body weight values and changes from baseline will be summarized at each scheduled time point.

Physical and Neurological Examination

The number and percentage of subjects with a change from normal at baseline to abnormal at any postbaseline exam will be tabulated by treatment group.

Subjects with abnormal findings will be presented in a data listing.

Dermatologic and Ophthalmologic Examination

Results of the dermatologic and ophthalmologic examinations (incl. OCT) will be presented by treatment group. Subjects with abnormal findings will be presented in a data listing.

Columbia Suicide Severity Rating Scale (C-SSRS)

Results from the C-SSRS will be tabulated by treatment group for all subjects receiving at least one dose of study drug in this study.

Safety MRI

The number and percentages of subjects with presence of ARIA-E, ARIA-H, and other MRI abnormalities found in the safety MRI assessments will be tabulated by treatment group.

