Abbreviations = CDR: Clinical Dementia Rating Scale; CFI: Cognitive Function Index; CSF: cerebrospinal fluid; C-SSRS: Columbia Suicide Severity Rating Scale; CVLT-II: California Verbal Learning Test – Second Edition; DRC: Data Review Committee; ECG: electrocardiogram ; MRI: Magnetic Resonance Imaging; MMSE: Mini Mental State Examination; OCT: Optical Coherence Tomography; PK: pharmacokinetic(s); PD: pharmacodynamics; RBANS: Repeatable Battery for the Assessment of Neuropsychological Status.

TIME AND EVENTS SCHEDULE (FOOTNOTES)

Footnotes

- ^a Subjects will self-administer study drug (once daily) with a glass of water following breakfast or a light snack. Study drug administration will take place during the morning hours. During scheduled visits when ECG or blood samples for JNJ-54861911 concentrations in plasma are to be obtained subjects will self-administer their study medication on site as described above. On Day 1 study drug administration will not be time limited.
- ^b Baseline (predose) only if no (adequate) assessment was obtained under the parent protocol at the last study visit of the treatment phase.
- ^c Must be performed predose.
- ^d At all time points, triplicate ECGs are required, i.e., 3 individual ECG tracings should be obtained as closely as possible in succession, but no more than 2 minutes apart. The full set of triplicates should be completed in less than 4 minutes.
- ^e Only if no adequate assessment was obtained under the parent protocol within 9 months of first dosing in this study.
- ^f May be performed during screening in case of logistical issues.
- ^g C-SSRS baseline: Only to be completed if no C-SSRS assessment was performed under the parent protocol; C-SSRS since last visit: to be completed if the C-SSRS assessment was performed under the parent protocol.
- ^h The RBANS will be completed first followed by the CDR and MMSE if the raters for RBANS and CDR are independent. If the raters for RBANS and CDR are the same, the CDR will be performed first, followed by the RBANS and MMSE.
- ⁱ Only if no adequate assessment was obtained under the parent protocol 6 months prior to first dosing in this study.

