1.1. Background

JNJ-54861911 is a BACE inhibitor being developed for the treatment of AD. JNJ-54861911 reduces production of A β fragments by inhibiting BACE1 processing of APP, with the aim of reducing AP formation. JNJ-54861911 has been demonstrated to be potency potent reducer of A β , both in nonclinical models, as well as in initial clinical studies.³⁷

Nonclinical Studies

Pharmacologic Profile

Safety Profile

[Redacted]

[Redacted]

[Redacted]

[Redacted]

[Redacted]

[Redacted]

Clinical Studies

For the most comprehensive clinical information regarding JNJ-54861911, refer to the latest version of the Investigator's Brochure for JNJ-54861911.³⁷

Study 54861911ALZ2004 will be an extension study for subjects in the early AD spectrum who have completed a Phase 1b or Phase 2 clinical trial with JNJ-54861911.

Study 54861911ALZ2004 is the third study in subjects in the early (predementia) AD spectrum following the proof of mechanism (POM) study (54861911ALZ1005) and the 6-month safety study (54861911ALZ2002). The POM study 54861911ALZ1005 is being performed to confirm a drug interaction with the intended enzyme (BACE) at the intended target location (brain) at the intended dose range (placebo q.d., 10 mg q.d. and 50 mg q.d. JNJ-54861911) following 1 month of treatment in subjects with early (predementia) AD, while the 6-month safety study (54861911ALZ2002) is being performed to provide safety information in preparation for the longer term treatment studies.

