Eligible subjects enrolled in this study will receive either JNJ-54861911 (10 mg or 25 mg q.d.) or placebo (q.d.). Subjects will continue with their current treatment regimen established in the parent JNJ-54861911 study (e.g. for 54861911ALZ2002 placebo or JNJ-54861911) for a period of 52 Weeks (12 Months) (placebo-controlled DB treatment phase). Subjects who have received an active dose different from 10-mg or 25-mg JNJ-54861911 in 54861911ALZ2002 study will be receiving the closest dose available in DB treatment phase (10-mg or 25-mg JNJ-54861911; e.g., subjects receiving 50 mg in study 54861911ALZ2002 will be assigned to 25 mg JNJ-54861911).

Following the initial 52-Week (12-Month) treatment phase (DB treatment phase) in this study, subjects receiving placebo in the DB treatment phase will be randomized with equal chance to one of 2 active JNJ-54861911 dose levels (i.e., 5-mg q.d JNJ-54861911 or 25-mg q.d. JNJ-54861911) for continuous treatment in OL phase. As such during OL phase, all subjects will receive active (JNJ-54861911) treatment (open-label). In addition, subjects who were receiving 10 mg q.d. JNJ-54861911 will have their dose reduced to 5 mg q.d. in order to harmonize the dosage with that of the Phase 2b/3 program, while subjects who were receiving 25 mg q.d. will continue to receive that dosage.

During the Treatment Phases (DB and OL treatment phases), primarily safety and tolerability will be monitored at regular intervals (e.g., MRI, physical and neurological examination, suicidality risk assessment, vital signs, 12-lead ECG, safety labs, dermatologic and ophthalmologic examinations). Pharmacokinetics (CSF and plasma), and PD effects by means of biomarkers (fluid [CSF and plasma samples] and imaging (volumetric MRI)) will be explored at the time points listed in the Time and Events Schedule. In addition, effects of JNJ-54861911 on cognition (e.g., Repeatable Battery for the Assessment of Neuropsychological Status (RBANS), Mini Mental State Examination (MMSE) and California Verbal Learning Test – Second Edition [CVLT-II]) will be assessed at regular intervals. The subject's clinical status will be assessed during the study by means of the Clinical Dementia Rating Scale (CDR). Investigators will

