9.1.3. Double-Blind Treatment Phase

Day 1

Subjects who successfully complete the screening examination will visit the clinical site on Day 1 of the DB treatment phase during the morning hours.

Prior to dosing following (baseline) assessments will be performed:

- C-SSRS (since last visit [or baseline if no C-SSRS was collected under the parent protocol])
- Blood sample collection for plasma JNJ-54861911 concentrations
- Blood sample collection for pharmacodynamics/biomarkers
- (Optional) CSF sample collection (~12 mL) by single lumbar puncture for PK/PD/biomarker assessment (baseline) after eligibility has been confirmed, provided no on-treatment sample was collected under the parent protocol
- 12-lead ECG recording
- Adverse event and concomitant medication will be reviewed

Following assessments will be performed prior to first dose in the current study at time points mentioned below only if no adequate assessments were conducted in ALZ2002 study (the assessments listed below 6 months and 9 months prior to dosing may also be performed during the screening period in case of any logistical issues):

1. At the last study visit of the treatment period:
 - Physical examination
 - Neurological examination
 - Body weight
 - Body temperature
 - Supine and standing vital signs (systolic and diastolic blood pressure and pulse)
 - Clinical safety laboratory assessments under fasted conditions, when feasible (including hematology, serum chemistry, and urinalysis)
2. 6 months prior to first dosing in this study (the assessments listed below may also be performed during the screening period in case of any logistical issues):
 - MRI
3. 9 months prior to first dosing in this study (the assessments listed below may also be performed during the screening period in case of any logistical issues):
 - Dermatological Examination

- Ophthalmological Examination (only in subjects completing the ALZ2002 parent study)
- Optical Coherence Tomography (OCT; at sites where OCT is available, in subjects completing the 54861911ALZ2002 parent study)

Eligible subjects will be assigned on Day 1 predose to the same treatment regimen in this study as received under 54861911ALZ2002 study as described in Section 6, Dosage and Administration.

Study medication will be dispensed (incl. drug accountability) and administered as outlined in Section 6, Dosage and Administration. Subjects will self-administer their study medication q.d. as instructed.

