On Day 1 dosing will not be time limited and will be performed following completion of the baseline (predose) assessments.

Following dosing on Day 1 following assessments will be performed:

- 12-lead ECG recording at 2 to 4 hours postdose
- Blood sample collection for plasma JNJ-54861911 concentrations at 2 to 4 hours postdose
- MMSE*
- CFI*
- CDR*
- RBANS*

** This assessment scheduled on Day 1 may be performed either predose or postdose provided they have not been collected under the parent protocol 1) at the last study visit of the treatment phase or 2) 6 months prior to first dosing in this extension study.*

During DB treatment phase, following Day 1, subjects will return to the investigational site at regular time points as indicated in the Time and Events Schedule and further described below.

Week 8

Subjects will visit the site at Week 8 during the morning hours. Study medication will be self-administered on site as outlined in Section 6, Dosage and Administration.

Clinical safety laboratory assessments (hematology and serum chemistry) will be performed under fasted conditions, when feasible, as specified in the Time and Events Schedule. Assessments can be performed pre or post dose unless otherwise indicated.

Week 12

Subjects will visit the site at Week 12 during the morning hours. Study medication will be self-administered on site as outlined in Section 6, Dosage and Administration.

The following assessments will be performed at Week 12 as specified in the Time and Events Schedule. Assessments can be performed pre or post dose unless otherwise indicated.

- Drug accountability/Treatment compliance will be assessed. Study medication received on Day 1 will be handed in and new medication will be dispensed.
- C-SSRS (since Day 1)
- CVLT-II, in subjects who had this assessment in the parent study
- Adverse events and concomitant medication will be reviewed

Week 16

Subjects will visit the site at Week 16 during the morning hours. Study medication will be self-administered on site as outlined in Section 6, Dosage and Administration.

Clinical safety laboratory assessments (hematology and serum chemistry) will be performed under fasted conditions, when feasible, as specified in the Time and Events Schedule. Assessments can be performed pre or post dose unless otherwise indicated.

Week 24

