Specific dermatologic and ophthalmologic examinations, as described in Section 9.2, Safety Evaluations, have been implemented in this study as potential BACE1- or BACE2-linked toxicities (e.g. melanin deposition changes and retinal abnormalities) have been described in the literature (e.g. BACE1 or BACE2 knock-out mice). With the exception of fur discoloration resulting in progressive lightening of the fur from normal dark brown to paler cream or grey, which was seen in one species only (Tg mice in the 6 month carcinogenicity study), these toxicities have not been observed in preclinical studies with JNJ-54861911.

Subjects participating in this study may have direct benefit as a consequence of the longer treatment duration, however to date efficacy of this compound has not been proven. Effects on slowing down the rate of cognitive decline are only expected to become apparent after a treatment duration of approximately 3 years based on evidence from previous longitudinal studies in this field (Alzheimer's Disease Neuroimaging Initiative [ADNI] and the Australian Imaging, Biomarkers and Lifestyle Flagship Study of Ageing [AIBL]).

A placebo arm is warranted and necessary to allow for an accurate assessment of the safety and tolerability of the study drug. The placebo arm will be limited in time to the first 12 months of this study. Combined with the duration of treatment under the parent protocols (e.g., 6 months) an additional 12-month placebo-controlled period in this study is deemed sufficient to assess any emergent safety aspects (treatment induced effects) of JNJ-54861911 in relation to placebo treatment. In addition at this moment there is no treatment available for subjects at risk for Alzheimer's dementia or subjects in the earliest AD spectrum so the use of placebo in an individual subject is not harmful, nor does it prevent them from the use of an indicated active treatment. Treatment with placebo dosing is not equivalent to non-treatment. All medication treatment will occur within the context of carefully supervised and supportive care.

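### The physical and neurological examination shift table starts from an on-treatment parent-study baseline, so persistent abnormalities that arose on drug in the parent study drop out of the active arms' count

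*Protocol*

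**What the plan says.** **Analysis rule.** For the physical and neurological examination, Section 11.5 reports, as number and percentage, "subjects with a change from normal at baseline to abnormal at any postbaseline exam will be tabulated by treatment group". For the ECG, intervals "will be summarized at baseline and at each scheduled time point and for changes from baseline using descriptive statistics", and QTc increases above 30 ms from baseline are counted by arm. Section 11.5 does not itself say which assessment is the baseline.

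**Baseline.** The Day 1 physical and neurological examination carries footnote b of the Time and Events Schedule: "Baseline (predose) only if no (adequate) assessment was obtained under the parent protocol at the last study visit of the treatment phase". Section 9.1.3 repeats the arrangement. The ECG has no such footnote. Section 9.1.3 lists a Day 1 ECG under "Prior to dosing following (baseline) assessments will be performed", followed by a "12-lead ECG recording at 2 to 4 hours postdose"; the Week 24 and Week 52 ECGs are also postdose.

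**Exposure before baseline.** Section 3.1: "Subjects will continue with their current treatment regimen established in the parent JNJ-54861911 study". Section 1.1 gives the parent's length: "the 6-month safety study (54861911ALZ2002) is being performed to provide safety information".

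**Intended window.** Section 16.1 argues that, combined with the parent treatment, "an additional 12-month placebo-controlled period in this study is deemed sufficient to assess any emergent safety aspects". Section 3.2 makes the same argument.

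**The concern.** The primary objective is long-term safety, and the protocol justifies the length of its placebo control by adding the parent period to the 52 weeks here. The examination shift table does not use that combined window. It restarts at the end of the parent treatment period.

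The restart affects the arms differently. Placebo subjects enter with a drug-free baseline. Active subjects enter with one taken after about 6 months of drug, so a drug-caused abnormality already present is treated as their starting state. The between-arm difference is then pulled toward zero in a table meant to show such differences.

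The plan handles related data differently. Section 11.5 brings adverse events from preceding studies into the adverse event summaries where appropriate, and Section 9.2.6 compares skin findings with the parent examinations where applicable.

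**Working it through.** The protocol has no figure to reproduce: there is no formal hypothesis (Section 2.2) and no sample size calculation (Section 11.2). The check applies the rule to example records and then sizes the loss under stated assumptions.

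**1. The rule applied.** Take two active-arm subjects, both normal before the parent study.
- Subject A has an abnormal vibration sense at the last parent visit (Month 6), still present at Week 52. Baseline is abnormal, so the shift count is 0.
- Subject B has the same finding first seen at Week 52. Baseline is normal, so the shift count is 1.

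Both are abnormal at Week 52 after about 18 months of drug. Only B enters the table.

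**2. Size for examinations.** Assumptions, not in the documents: an 18-month excess risk R of 5%, 10% or 20%, constant hazard, findings that persist. The part arising in the 6 parent months is 1 − (1 − R)^(6/18).

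| R | arises in months 0–6 | left in the shift table | share lost |
|---|---|---|---|
| 5% | 1.70% | 3.3% | 33.9% |
| 10% | 3.45% | 6.6% | 34.5% |
| 20% | 7.17% | 12.8% | 35.8% |

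This is essentially 6 months out of 18. If onset is earlier, more is lost: with a true 10%, and 50%, 75% or 100% of cases arising and persisting in the parent period, the table shows 5.0%, 2.5% or 0%. If findings resolve before baseline, less is lost.

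**3. Size for QTc.** Inputs: multiple-dose half-life 14.4 to 18.5 h and time to peak 2 to 4 h (Section 1.1); a maximum mean effect of 6.6 ms at 50 mg, and an expected effect well below 5 ms at 25 mg (Section 1.2). Assumption: the effect is proportional to plasma concentration.

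Fraction of peak left at a 24 h trough = exp(−ln 2 × (24 − tmax) / half-life):
- half-life 14.4 h: 0.347 (tmax 2 h) to 0.382 (tmax 4 h)
- half-life 18.5 h: 0.439 to 0.473

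Average rise in a predose baseline with no treatment gap:
- 5 ms taken as an upper bound for 25 mg: 5 × 0.347 to 5 × 0.473 = 1.7 to 2.4 ms
- 6.6 ms, for subjects arriving from 50 mg: 6.6 × 0.347 to 6.6 × 0.473 = 2.3 to 3.1 ms

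After 7 days off drug the fraction is exp(−ln 2 × 168 / half-life) = 0.0003 to 0.0018, below 0.2%. Enrolment may follow parent treatment by up to 6 weeks, or 12 with sponsor approval (Section 4.1), so many baselines could be washed out. Later ECGs fall near peak, so most of an acute effect still shows as change.

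**The case against.** The strongest objection is that the analysis baseline is inferred. Section 11.5 names none, footnote b sits in a visit schedule and says when an examination must be repeated, and Section 11 calls itself a general description. A statistical analysis plan, not shown here, could use a pre-drug parent baseline. That possibility stands. But the protocol does identify a baseline, and uses the word in the same way elsewhere: Section 9.2.7 lets the parent eye assessments serve as baseline, and Section 9.3.1.1 the parent on-treatment CSF sample. An analyst who follows the protocol gets the biased table.

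A reader might infer that such abnormalities are never counted anywhere. The documents do not support that. Section 11.5 lists all subjects with abnormal findings whatever their baseline, and parent adverse events enter the adverse event summaries where appropriate. The parent is itself placebo-controlled, so months 0 to 6 have their own comparison. Still, a listing gives no rate by arm, the adverse event route needs the finding to have been reported as an event, and neither corrects the shift table.

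A reader might also infer that QTc signals are substantially hidden. They are not: the average masking is about 3 ms at most against a 30 ms threshold, absolute values above 450, 480 and 500 ms are still reported, and a direct switch without a gap is possible but not established as the usual case.

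Finally, enrolled subjects are self-selected parent completers. No choice of baseline recovers those who left the parent study because of an abnormality.

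**Conclusion.** The point holds for the by-arm examination shift table. With the baseline the protocol identifies, an abnormality that arises on active drug in the parent study and persists is excluded from the active arms' count, while placebo subjects start drug-free. The direction, toward no difference, needs only that some drug-caused findings arise in the parent period and persist. The size is not known: about one third of the excess under constant hazard and full persistence, more with early onset, less if findings resolve.

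For ECG change from baseline the same mechanism is minor: at most about 3 ms on average with no gap, under proportionality to concentration, and negligible after a week or more. Individual subjects may differ from the average.

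Separately, the QTcF criterion in Sections 3.4.1 and 10.2 refers to an increase versus baseline without naming the baseline. Those sections and Section 11.5 must be reconciled; which baseline the stopping criterion should use is not a matter for this point.

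**What to change.** In Section 11.5, for the double-blind phase:
- Add an examination-shift table by treatment group taken from the last assessment before the first parent dose, beside the table from this study's baseline, and name the baseline in each title.
- Secondarily, give ECG change from the same pre-dose assessment.
- Flag subjects with no usable parent pre-dose record and report how many there are in each arm.
- State which baseline the phrase in Sections 3.4.1 and 10.2 refers to, so that those sections and the tables can be read together.

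The cost is a merge of parent-study records and two more tables. No new visits or data collection are needed. The downside is that some subjects may lack a usable pre-dose record, and the documents do not describe the parent's pre-dose examination or ECG methods, so comparability has to be checked before the merge.
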